5.5. Warning and Precautions

LMIS 25 mg contains the active pharmaceutical ingredient of leuprolide. Thus, the use of LMIS 25 mg may cause adverse events similar to the established AE profiles observed in the use of leuprolide acetate.

Leuprolide acetate has the following established significant AEs:

- Transient clinical testosterone flare reaction in men with prostate cancer
- Osteoporosis

Like other LH-RH analogs, leuprolide acetate causes a transient increase in the serum concentration of testosterone during the first week of treatment. This effect may cause subjects to experience a worsening of symptoms or an onset of new symptoms including bone pain, neuropathy, hematuria, or ureteral or bladder outlet obstruction. Long-term use of an LH-RH agonist has been reported to decrease bone mineral density which can increase the risk of osteoporosis and skeletal bone fractures.

Other reported adverse events of leuprolide acetate include hypogonadism, reduction in glucose tolerance, metabolic syndrome, anemia, and prolongation of the QT/QTc interval.

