11.5 Other Variables Related to Safety

Concomitant Medication and Non-Drug Therapy

Individual subject concomitant medication and non-drug therapy will be listed in [Listing 16.2.5.2](#).

12-Lead ECG

Individual subject 12-Lead ECG data (heart rate, PR interval, RR interval, QRS duration, QT, QTc and overall interpretation) will be listed in Listing 16.4.3.

The baseline is defined as the last observation prior to first dose unless otherwise specified. The summary results of 12-lead resting ECG at baseline, EOS/ET Visit will be summarized descriptively in Table 14.3.8.1. The transition matrix for ECGs overall interpretation (normal, abnormal NCS and abnormal CS status) will be summarized in Table 14.3.8.2.

Additional 12-Lead ECG and PK Analyses for ECG Report

A separate ECG report will be provided with the results of the analyses in this section.

The following corrected QT interval for each visit and time point will be derived and considered the primary ECG assessment for the analysis in the ECG report.

QTcF: The QT interval in units of milliseconds (msec) corrected by the Fridericia formula will be calculated as follows:

$$QTcF = \frac{QT}{\sqrt[3]{RR}}, \text{ where RR interval will be expressed in units of seconds.}$$

Descriptive statistics (number of subjects, mean, SD, 2-sided CI [90% for the QTcF interval or 95% for other parameters], median, 25th percentile, 75th percentile, minimum, and maximum) will be provided for baseline and each visit and time point post dose for results and change from baseline, denoted as ΔECG (i.e. $\Delta QTcF$, ΔHR , ΔPR , ΔQRS), for the ECG population. Missing data will not be imputed. Unscheduled data will not be summarized or included in analyses. The means and 90% (in the case of $\Delta QTcF$) or 95% CIs for the ΔHR , ΔPR , and ΔQRS values, will be displayed graphically by scheduled day and time point.

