- BASEADJ represents the numeric baseline minus the overall mean of all baseline values for the ECG parameter;
- TYPE=UN means that an unstructured covariance matrix will be used for the correlated random effects (INTERCEPT and CONC);
- xx.x in the ESTIMATE statement represents the estimated arithmetic mean C_{max} for leuprolide or testosterone.

Categorical Analyses for ECG Report

Categorical analyses of HR, PR, QRS, and QTcF will be performed to determine the number and percentage of subjects, who meet each of the following criteria at each day/time point and at the maximum/minimum QTcF (HR, PR or QRS) value postdose:

- Result QTcF ≤ 450 , >450 and ≤ 480 , >480 and ≤ 500 , and >500 msec;

Statistical Analysis Plan

- Change from baseline $\Delta\text{QTcF} \leq 30$, >30 and ≤ 60 , and >60 msec;
- PR Outliers (PR >200 msec and a 25% or greater increase from baseline);
- QRS Outliers (QRS >100 msec and a 25% or greater increase from baseline);
- HR Outliers (HR <50 beats/min and a 25% or greater decrease from baseline);
- HR Outliers (HR >100 beats/min and a 25% or greater increase from baseline).

Morphological ECG Diagnostic Statement Analyses for ECG Report

Abnormal morphological diagnostic statements will be tallied and tabulated for each day/time point and overall. The incidence rate of abnormal diagnostic statements will be tabulated for both baseline and post dose assessments, and also tabulated with abnormal diagnostic statements categorized as treatment emergent diagnostic statements (i.e., abnormal diagnostic statements not present on the baseline assessments). The variety of morphology statements with the same meaning will be aggregated into defined categories by the Cardiac Safety Expert and incorporated into the analysis dataset. For example, T-wave inversion in Lead V2 and T wave flattening in Lead II will both be categorized as nonspecific T-wave abnormality.

Adequacy of HR Correction for ECG Report

The adequacy of the correction formula for QTcF will be assessed by determining the linear relationship of QTcF interval to RR. Adequacy will be defined as a population QTcF:RR slope of $< |0.045|$, and a slope of $< |0.045|$ in at least 50% of individual subjects. If QTcF interval is determined to be an inadequate correction, the QT interval with a study specific QTcSS will be calculated.

ECOG Performance Status

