Individual subject ECOG performance status will be listed in Listing 16.4.4. The ECOG performance status will be summarized descriptively as Table 14.1.2.

Local Injection Site Reaction

Individual subject Local Injection Site Reaction will be listed in Listing 16.4.5. The local injection site reaction as recorded by Grade 0 (None), Grade 1 (Mild), Grade 2 (Moderate) and Grade 3 (Severe) will be summarized descriptively as count and percentage as Table 14.3.9.

Bone pain and urinary sign and symptoms (I-PSS)

Individual subject Bone pain and urinary sign and symptoms will be listed in Listing 16.4.6~ Listing 16.4.8. The summary results of VAS scale for bone pain measurement at baseline, EOS/ET Visit

Statistical Analysis Plan

and the change from baseline will be summarized descriptively in Table 14.3.10.1. Also, the change from baseline to EOS/ET visit will be tested by paired t-test or Wilcoxon signed-rank test at a significance level of 0.05. The urinary sign and symptoms at baseline and EOS/ET Visit will be summarized descriptively as Table 14.3.10.1. The transition status for urinary sign and symptoms by each scale* will be presented as Table 14.3.10.2. The quality of life will be presented as Table 14.3.10.3.

*For Urinary signs and symptoms Q1-Q6: 0 - None, 1 - Less than 1 time in 5, 2 - Less than half the time, 3 - About half the time, 4 - More than half the time, and 5 - Almost always.

For Urinary signs and symptoms Q7: 0 - None, 1 - 1 time, 2 - 2 times, 3 - 3 times, 4 - 4 times, 5 - 5 or more times.

For Urinary signs and symptoms quality of life: 0 - Delighted, 1 - Pleased, 2 - Mostly Satisfied, 3 - Mixed, 4 - Mostly Dissatisfied, 5 - Unhappy, 6 - Terrible

Unscheduled Assessments

The unscheduled assessment will be listed in Listing 16.4.9.

Telephone Contact

The telephone contact information will be listed in Listing 16.4.10.

12.COMPUTER METHODS

All statistical analyses will be conducted using SAS[®] software, Version 9.3 of the SAS System for Windows 7. Copyright[©] 2013 SAS Institute Inc. SAS and all other SAS Institute Inc. product or service names are registered trademarks or trademarks of SAS Institute Inc., Cary, NC, USA.

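### As written, the ECG report's rule on unscheduled ECGs also removes them from the worst post-dose outlier counts and the overall morphology tallies

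*SAP*

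**What the plan says.** SAP 11.5, under the heading for additional ECG and PK analyses, opens with "A separate ECG report will be provided with the results of the analyses in this section". The paragraph on descriptive statistics by visit and time point then states, without qualification: "Unscheduled data will not be summarized or included in analyses".

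Later in SAP 11.5, the categorical analyses for the same report count subjects "who meet each of the following criteria at each day/time point and at the maximum/minimum QTcF (HR, PR or QRS) value postdose". The first criterion is "Result QTcF ≤ 450 , >450 and ≤ 480 , >480 and ≤ 500 , and >500 msec". The others are bands for change in QTcF, the highest being above 60 msec, and outlier definitions for PR, QRS and HR. The morphology analyses tally abnormal diagnostic statements by time point and overall, and separately those not present at baseline (treatment emergent). Neither block mentions unscheduled ECGs.

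Elsewhere in SAP 11.5, unscheduled assessments of all kinds receive one line: "The unscheduled assessment will be listed in Listing 16.4.9". The main-report ECG table does not pick them up: "The summary results of 12-lead resting ECG at baseline, EOS/ET Visit will be summarized descriptively in Table 14.3.8.1".

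**The concern.** Leaving unscheduled ECGs out of by-visit means and out of the concentration-ECG model is ordinary practice: they belong to no nominal time point and need have no time-matched concentration. A worst-value table has a different purpose. It should show the most extreme value recorded for each subject after dosing, and a maximum taken over scheduled tracings only is not that.

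Protocol 5.5 names "prolongation of the QT/QTc interval" among the reported adverse events of leuprolide acetate. SAP section 2 makes ECG effects a secondary objective, and SAP 3.3 lists change in QTcF as a safety endpoint. The counts above 500 msec and above a 60 msec increase are therefore figures a safety reader will look for. If they silently omit recorded post-dose values, the table's label promises more than it delivers.

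**Working it through.** The plan attaches no figure to this rule, so there is nothing to reproduce. The check has three parts.

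**1. Which ECGs can enter the maximum.** Protocol 7.3.5 and the study schedule give these ECGs after the first dose: Day 0 at 4 hours, Day 28, Day 84 before dosing, Day 84 at 4 hours, and Day 168 or early termination. That is 5 at most, and fewer for a subject who leaves early. For a subject on schedule, the intervals without a scheduled ECG are:

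- Day 0 to Day 28: 28 days
- Day 28 to Day 84: 84 − 28 = 56 days
- Day 84 to Day 168: 168 − 84 = 84 days

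Within those intervals, only an unscheduled ECG could record a value.

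**2. Direction of the effect.** Let S be a subject's scheduled post-dose QTcF values and U his unscheduled ones. With baseline held fixed, max(S and U together) ≥ max(S). Adding U can therefore move a subject into the top category (above 500 msec, or change above 60 msec) but never out of it, so exclusion can only lower those counts or leave them unchanged. The same argument applies to the minimum for the low-HR criterion. It does not apply to the intermediate QTcF bands, where a subject may leave one band for a higher one. A repeat of an already abnormal scheduled post-dose tracing changes nothing unless it crosses a further threshold. The subjects at issue are those who cross a threshold *only* on an unscheduled ECG.

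**3. Illustration of size (assumed counts).** Let k be the number of subjects with QTcF above 500 msec only on an unscheduled ECG, with no other subject above 500 msec. Take n = 144, the enrolment stated in SAP 4.4. The actual denominator would presumably be the ECG population of SAP 6.4, whose size is not given. Exact (Clopper-Pearson) 95% limits:

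- lower = Beta quantile at 0.025 with parameters k and n − k + 1 (0 when k = 0)
- upper = Beta quantile at 0.975 with parameters k + 1 and n − k

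For k = 0 the upper limit reduces to 1 − 0.025^(1/144) = 2.5%.

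| k | k/144 | exact 95% CI |
|---|---|---|
| 0 (what the table would show) | 0% | 0 to 2.5% |
| 1 | 0.7% | 0.02 to 3.8% |
| 2 | 1.4% | 0.2 to 4.9% |
| 3 | 2.1% | 0.4 to 6.0% |

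The intervals overlap heavily. What changes is whether the table reports any such case at all.

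**The case against.** The best defence concerns scope. The sentence stands in a paragraph on statistics for each visit and time point, between a statement that missing data are not imputed and a sentence on plots by scheduled day and time. The outlier analysis has its own heading, and its maximum/minimum is set beside the by-time-point counts without being limited to scheduled tracings. The sponsor may have meant the exclusion for by-visit summaries only. That reading is possible and cannot be ruled out. Against it, the rule bars inclusion in analyses without limit, the part of the section it stands in is introduced as covering the ECG report, and nothing later restores these records. A programmer following the text would drop them. If the narrow reading was intended, the text still needs to say so.

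Two stronger inferences are tempting, and the documents support neither.

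- *Unscheduled ECGs are prompted by symptoms or earlier abnormal tracings, so the most informative values are lost.* No section says why or how often such ECGs are taken. Protocol 7.2.1 and 7.2.2 provide for extra testosterone, LH and PSA tests at the investigator's discretion; Protocol 7.3.5 has no matching provision for ECGs. There may be none.
- *Such findings go unreported.* Unscheduled assessments are listed. Protocol 9.1 requires all adverse events to be recorded, including those detected through other assessments, and SAP 11.1 tabulates the treatment-emergent ones. Clinically significant ECG changes as judged by the investigator are a safety endpoint in both documents. An ECG at early termination counts as scheduled.

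**Conclusion.** The point holds as a defect in a stated rule, with moderate confidence. On the plain reading, the worst-value outlier counts and the overall and treatment-emergent morphology tallies rest on at most five scheduled post-dose ECGs per subject, and any resulting error in the upper QTcF counts runs one way.

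Its size cannot be determined from the documents and may be zero. The figures for 1 to 3 subjects of 144 are assumptions that show scale; they are not estimates. A reader might infer that the ECG report will understate QT risk. The supportable statement is that it could, if some subject crosses a threshold only on an unscheduled ECG.

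The effect is confined to descriptive safety counts in the ECG report. The primary efficacy analysis, the by-visit ECG means and the concentration-ECG model are untouched. This should be corrected, but it does not threaten the trial's main conclusions.

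**What to change.** In SAP 11.5, replace the sentence with:

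> Unscheduled ECGs are excluded from by-time-point summaries and the concentration-ECG model but are included in the maximum/minimum post-dose categorical analyses and in the overall and treatment-emergent morphology counts.

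The cost is one SAP sentence and the matching programming. No new data are collected and no other analysis changes. The downside is that outlier and morphology counts may rise slightly.

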3.4 Study Population

Inclusion Criteria

Subjects must meet all of the following inclusion criteria to be eligible for enrollment into the study:

1. Males aged ≥ 18 years old
2. Males with histologically confirmed cancer of the prostate
3. Subjects who are judged by the attending physician and/or principal investigator to be a candidate for androgen ablation therapy
4. Baseline morning serum testosterone level > 150 ng/dL performed at screening visit
5. Eastern Cooperative Oncology Group (ECOG) Performance score ≤ 2
6. Life expectancy of at least 18 months
7. Laboratory values
 - Absolute neutrophil count $\geq 1,500$ cells/ μ L
 - Platelets $\geq 100,000$ cells/ μ L
 - Hemoglobin ≥ 10 gm/dL
 - Total bilirubin $\leq 1.5 \times$ upper limit of normal (ULN)
 - AST (SGOT) $\leq 2.5 \times$ ULN
 - ALT (SGPT) $\leq 2.5 \times$ ULN
 - Serum creatinine ≤ 1.5 mg/dL
 - Lipid profile within acceptable range according to investigator's opinion

- Serum glucose within acceptable range according to investigator's opinion
 - HbA1c $\leq 9.5\%$
 - Clinical chemistries (K, Na, Mg, Ca and P) within acceptable range according to investigator's opinion
 - Normal urinalysis results within:
 - ✓ RBCs ≤ 3 RBCs/hpf
 - ✓ WBCs ≤ 5 WBCs/hpf
 - ✓ Nitrate: negative
 - ✓ Glucose: <0.1 g/dL; but <1.0 g/dL in subjects with diabetes mellitus
8. Agree to use male contraceptive methods during study trial
 9. In the investigator's opinion, the ability to understand the nature of the study and any hazards of participation, and to communicate satisfactorily with the investigator and to participate in, and to comply with, the requirements of the entire protocol
 10. All aspects of the protocol explained and written informed consent obtained

Exclusion Criteria

Subjects presenting with any of the following will not be included in the present study.

1. Receipt of chemotherapy, immunotherapy, cryotherapy, radiotherapy, or anti-androgen therapy concomitantly, or within 8 weeks prior to screening visit, for treatment of Cancer of the prostate. Radiation for pain control will be allowed during the study.
2. Receipt of any vaccination (including influenza) within 4 weeks of screening visit
3. History of blood donation within 2 months of screening visit
4. History of anaphylaxis to any LH-RH analogues
5. Receipt of any LH-RH suppressive therapy within 6 months of screening visit
6. Patients who were previously enrolled in the LMIS 50 mg study

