An analysis will be provided for the PK/ECG population based on a linear mixed effects model. The mixed-effects model will contain $\Delta QTcF$ as the dependent variable and include the corresponding leuprolide or testosterone serum concentrations in separate models with a random intercept and slope, day/time point as a categorical variable, and baseline QTcF (adjusted for the overall mean of subjects' baseline data included in the model) as the independent variables. The mixed effects model will be used to estimate, for all subjects in the PK/ECG analysis population, the predicted population mean $\Delta QTcF$ and its corresponding 2-sided 90% CI at mean C_{max} of the serum concentrations. Serum concentration values reported as below the limit of quantitation (BLQ) will be assigned a value of zero in this analysis. This analysis will be repeated for ΔHR , ΔPR , and ΔQRS , but 95% CIs will be presented rather than 90%.

Statistical Analysis Plan

The adequacy of the linear assumption between Δ ECG interval and serum concentrations will be determined by adding a quadratic term to the mixed-effects model. If the quadratic term is different than zero, having a p-value <0.05 , and an Akaike's information criteria (AIC) that is smaller in comparison to the linear model's AIC, then a quadratic term may be added. In addition, a transformation of the concentrations [e.g. $\log(\text{Concentration}/\text{LLOQ})$, where LLOQ is the lower limit of quantitation of the assay and all values below the LLOQ are replaced with the LLOQ] may also be assessed. The best model fit will be determined by the lowest AIC, unless the model results are not clinically or physiologically sensible.

If convergence cannot be reached, adjustment to the model as follows will be considered: the random slope may be removed, an alternative covariance structure attempted, or as a last resort, the removal of the time effect may be considered.

The relevant SAS code statements are:

```
PROC MIXED DATA = DATA METHOD=REML;
  CLASS SUBJID ATPTN;
  MODEL CHG = CONC ATPTN BASEADJ /NOINT SOLUTION OUTP=PRED;
  RANDOM INTERCEPT CONC /TYPE=UN SUBJECT=SUBJID;
  ESTIMATE ' $\Delta$ ECG at Cmax' CONC xx.x / CL ALPHA=0.1;
RUN;
```

In the above statements:

- CHG represents the Δ QTcF value (or corresponding secondary parameter);
- CONC represents measured serum concentrations of leuprolide or testosterone;
- ATPTN represents the day/time point;

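### If testosterone affects QTcF, the SAP's testosterone-ECG models will tend to underestimate the slope, because they regress ECG change on the absolute level and omit baseline testosterone

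*SAP*

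**What the plan says.** SAP 11.5, in the part on additional ECG and PK analyses, models change from baseline in QTcF by a linear mixed model and will "include the corresponding leuprolide or testosterone serum concentrations in separate models with a random intercept and slope". The remaining terms are day/time point and "baseline QTcF (adjusted for the overall mean of subjects' baseline data included in the model) as the independent variables". The code agrees with the text: "MODEL CHG = CONC ATPTN BASEADJ /NOINT SOLUTION OUTP=PRED", with "RANDOM INTERCEPT CONC /TYPE=UN SUBJECT=SUBJID".

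The legend settles two points. First, "CONC represents measured serum concentrations of leuprolide or testosterone", so the predictor is the level at that visit and not a change. Second, "BASEADJ represents the numeric baseline minus the overall mean of all baseline values for the ECG parameter", so the only baseline in the model is that of the ECG parameter. One set of statements serves both analytes, and the analysis is repeated for HR, PR and QRS.

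The reported figure comes from the ESTIMATE statement, "CONC xx.x / CL ALPHA=0.1". It is the slope times the mean Cmax, with a 90% interval for QTcF.

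On the starting level, SAP 3.4 requires "Baseline morning serum testosterone level > 150 ng/dL performed at screening visit" and sets no upper limit. Protocol 7.3.5 schedules ECGs on Day 0 (pre-dose and 4 h), Day 28, Day 84 (pre-dose and 4 h) and Day 168. SAP 3.1 schedules a testosterone sample for every subject at each of those times.

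**The concern.** A change in the outcome is paired with a level in the predictor. For leuprolide the two match, because a pre-dose level of about zero makes level and change the same. Testosterone is endogenous and each man starts from his own value. That value is left out of the model, and it tracks the predictor mainly at the Day 0 4-hour ECG, the one scheduled post-dose ECG taken before suppression.

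At stake is the secondary objective in SAP section 2 on ECG effects in relation to leuprolide and testosterone, and the matching endpoint in SAP 3.3. Protocol 5.5 lists QT/QTc prolongation among reported events of leuprolide acetate, so a non-zero slope is plausible. An error toward zero would understate the effect per ng/dL, and the ESTIMATE statement would carry it straight into the reported figure.

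**Working it through.** **1. The plan's own figures.** The plan gives no slope, variance or power for the ECG model. Its only sample-size figure is for the primary test (120 subjects, 0.90 against 0.97, one-sided 0.025). Success at 115/120 or more has exact alpha 0.0160 and power 84.7%, against 85% stated. That reproduces, but it plays no part below.

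**2. Where the bias comes from.** Let QTcF = a + bT + e within a man, with T0, Q0 and e0 the baseline testosterone, QTcF and error. Then

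change in QTcF = bT - bT0 + e - e0.

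The SAP model has bT but no T0, so -bT0 falls into the random intercept. That intercept is assumed independent of the predictor, yet T0 and the 4-hour level are positively correlated. The bias therefore has the opposite sign to b.

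Two men illustrate this, with b = -0.02 ms per ng/dL and a 4-hour level of 1.2 x baseline (both assumed):

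| Man | T0 | T at 4 h | T castrate | Change at 4 h | Change castrate |
|---|---|---|---|---|---|
| A | 200 | 240 | 10 | -0.02 x 40 = -0.8 | -0.02 x (-190) = +3.8 |
| B | 800 | 960 | 10 | -0.02 x 160 = -3.2 | -0.02 x (-790) = +15.8 |

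- Comparing the men's own swings: (-19.0 + 4.6)/(950 - 230) = -14.4/720 = -0.02, which is right.
- Comparing the men at 4 h: (-3.2 + 0.8)/(960 - 240) = -2.4/720 = -0.0033, one sixth of b (1 - 1/1.2).

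The mixed model blends both kinds of information, so it lands between them.

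**3. Does baseline QTcF stand in for T0?** Hardly. With a testosterone SD of 150, bT0 has SD 0.02 x 150 = 3 ms. Between-man SD 18 and within-man SD 8 ms (assumed) give baseline QTcF an SD of sqrt(324 + 9 + 64) = 19.9 ms. The correlation in size is 3/19.9 = 0.15.

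**4. Simulation of the model as coded** (REML, 1000 trials per setting, five post-dose ECG times).

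From the documents: n = 144 enrolled (SAP 4.4); Day 28 mean testosterone of 17.6 ng/dL in the 50 mg study (Protocol 1.3), against about 14 used after suppression.

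Assumed, with ranges:
- baseline testosterone mean 400, SD 150 (100 to 200) ng/dL
- 4-hour ratio 1.2 (1.0 to 1.5), log-SD 0.2 (0.1 to 0.4)
- within-man SD 8 (5 to 12) ms, between-man SD 18 (10) ms
- slope -0.02 (0, -0.01, -0.04, +0.02) ms per ng/dL
- SD of slopes between men 0 (0.01, 0.02)

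Each cell is estimate/truth and coverage of the 90% interval.

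| Setting | SAP model | Plus centred T0 | Change in T, no T0 |
|---|---|---|---|
| Base case | 0.89, 83.3% | 1.00, 92.6% | 0.94, 88.4% |
| Slope -0.01 | 0.89, 89.3% | 1.01, 92.6% | 0.94, 90.5% |
| Slope -0.04 | 0.90, 68.3% | 1.00, 92.6% | 0.94, 81.5% |
| 4-hour log-SD 0.1 | 0.86, 80.1% | 1.01, 92.0% | 0.93, 88.3% |
| 4-hour log-SD 0.4 | 0.94, 86.0% | 1.00, 91.9% | 0.97, 89.7% |
| Within-man SD 5 | 0.89, 71.4% | 1.00, 92.7% | 0.98, 90.4% |
| Within-man SD 12 | 0.89, 88.1% | 1.01, 92.8% | 0.88, 86.2% |
| Between-man SD 10 | 0.90, 85.2% | 1.00, 92.9% | 0.84, 72.6% |
| Slopes vary, SD 0.01 | 0.78, 71.9% | 1.00, 89.6% | 0.93, 87.8% |
| Slopes vary, SD 0.02 | 0.64, 62.0% | 0.99, 88.5% | 0.91, 87.8% |

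With a true slope of zero the SAP model is unbiased, with coverage 92.5% (90.2% with slope SD 0.01). At n = 133 and 120 the base case gives 0.89 and 0.88, with coverage 83.4% and 82.1%.

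**5. Check on the base-case coverage.** Per 100 ng/dL the bias is 2.00 - 1.77 = 0.23 ms, the mean SE 0.365 and the SD of the estimates 0.367. The half-width is 1.645 x 0.365 = 0.60. Coverage is about Phi((0.60 - 0.23)/0.367) - Phi((-0.60 - 0.23)/0.367) = Phi(1.01) - Phi(-2.26) = 0.83, as simulated.

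**6. Why change in testosterone alone is not enough.** Baseline QTcF is also a covariate, and it contains bT0. Given Q0 and T0, the expected baseline error is k(Q0 - mean - bT0), with k = within-variance/(within + between variance). The correct coefficient on T0 is then -b(1 - k). In the base case k = 64/(64 + 324) = 0.165, so it is -0.835b. The SAP model forces it to 0 and change-only forces it to -b; a free covariate lets the data set it. The table follows k: change-only is best at within-man SD 5 (k = 25/349 = 0.07) and worst at between-man SD 10 (k = 64/164 = 0.39).

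**The case against.** The strongest reply is that the bias is conditional and modest. It vanishes at a zero slope, and at -0.01 ms per ng/dL coverage is 89.3% against a nominal 90%. In the base case the shortfall is 0.23 ms per 100 ng/dL, or 4 x 0.23 = 0.92 ms of an 8 ms effect over a 400 ng/dL fall. That is 0.23/0.367 = 0.6 of the estimate's own sampling SD. All of this stands, and the documents supply no slope or variances with which to narrow the range.

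The random intercept also does real work. A reader might infer that the model treats two castrate men with different starting values as if they had changed equally. It does not: each man's offset is constant and goes into his intercept. The fault is only that this intercept is correlated with the 4-hour level.

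A reader might go further and infer that every QTcF effect of lowering testosterone will be understated in the ECG report. The documents do not support that. SAP 11.5 also reports mean QTcF change with 90% intervals at each scheduled ECG time, and categorical outlier counts. Neither uses this slope. Nor do they support the reading that a test of zero slope is invalid.

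Finally, dropping the time factor, which the SAP allows as a last resort for non-convergence, gave 0.97 to 0.99 of the slope in simulation (run without a random slope). But the simulation contains no time effect, so this is no defence of the model.

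**Conclusion.** The concern holds in conditional form. If testosterone affects QTcF, the testosterone model as written tends to underestimate the slope, and its 90% interval tends to under-cover. Under the assumed inputs the slope is about 6-14% too small when common to all men (coverage about 68-89%) and about 22-36% too small when it varies between men, as the SAP's random slope allows (coverage about 62-72%). If the true slope is zero there is neither bias nor under-coverage.

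The direction follows from the algebra, given a linear effect and a positive correlation between baseline and the 4-hour level. The size rests wholly on the assumptions listed. The omission carries over to the HR, PR and QRS models by the same algebra, though only QTcF was simulated. The effect is confined to testosterone slopes and quantities built on them, in a secondary safety analysis.

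**What to change.** In the testosterone models for QTcF, HR, PR and QRS, add Day 0 pre-dose testosterone, centred at its mean, as a fixed covariate beside the centred ECG baseline. If the SAP's model-selection rule leads to a transformed or quadratic concentration term, enter baseline testosterone in the matching form. Reword the ESTIMATE so that it multiplies the slope by a change in testosterone fixed in advance and stated in the table title.

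Replacing the level by change in testosterone should not be the main fix: alone it recovered only 0.84 to 0.98 of the slope, with coverage of about 73% to 90%. The model without the covariate can stay as a supportive analysis. The leuprolide models need no change.

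The cost is a few lines of SAP text, one derived variable and one extra model term. The sample is already scheduled for every subject, and SAP section 4 already defines baseline as the last value before the first dose.

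### Selecting the concentration–ECG model by AIC from REML fits makes the choice between linear, quadratic and log forms depend on the unit of concentration

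*SAP*

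**What the plan says.** The text is in SAP 11.5, under the additional ECG and PK analyses for the ECG report.

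- **Estimation.** The code opens with "PROC MIXED DATA = DATA METHOD=REML". The fixed effects are "MODEL CHG = CONC ATPTN BASEADJ /NOINT SOLUTION OUTP=PRED" and the random effects are "RANDOM INTERCEPT CONC /TYPE=UN SUBJECT=SUBJID". Concentration enters in its raw unit.
- **Quadratic term.** It may be added if it differs from zero, "having a p-value <0.05 , and an Akaike's information criteria (AIC) that is smaller in comparison to the linear model's AIC".
- **Log form.** A transformation such as log(Concentration/LLOQ) may also be assessed, "where LLOQ is the lower limit of quantitation of the assay and all values below the LLOQ are replaced with the LLOQ".
- **Final choice.** "The best model fit will be determined by the lowest AIC", with an exception for results that are implausible on clinical or physiological grounds.

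The section specifies no ML fit for the comparison, no standardisation of concentration and no concentration unit. Testosterone is in ng/dL elsewhere in the documents; no unit for leuprolide concentration was found. The PK analysis plan is outside the SAP (SAP 1).

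The chosen model gives the predicted mean change in QTcF, with its 90% CI, at mean Cmax. SAP 2 makes the relation of ECG effects to leuprolide and testosterone concentrations a secondary objective, and SAP 3.3 lists it among the secondary safety endpoints. With two analytes and four ECG parameters (QTcF, HR, PR, QRS), the rule can be applied 2 × 4 = 8 times.

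**The concern.** AIC can compare models with different fixed effects only if all the likelihoods refer to the same data. An ML likelihood does. A REML likelihood is the likelihood of the data after the fixed effects have been projected out, so changing the fixed effects changes what it is a likelihood of. In the formula this shows up as a term in the determinant of X′V⁻¹X, which depends on which columns are in X and on their scale.

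The three candidates differ in exactly this way: one concentration column, two columns, or a different column. The comparison therefore carries an offset set by the unit of measurement and not by fit. The same data could give a different model, and so a different QTcF estimate and interval at mean Cmax, solely because the laboratory reports in pg/mL and not ng/mL. Protocol 5.5 lists QT/QTc prolongation among the reported effects of leuprolide acetate, so this result will be read.

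**Working it through.** The SAP states no figure for this rule, so there is none to reproduce. The check is algebra, confirmed by refitting.

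**1. Criterion.** With n observations and p fixed effects,

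−2RLL = log det V + log det(X′V⁻¹X) + r′V⁻¹r + (n − p) log 2π, and AIC = −2RLL + 2q.

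Under REML, PROC MIXED counts only covariance parameters in q. Here q = 4 (intercept variance, slope variance, their covariance, residual) for every candidate, so the extra quadratic coefficient carries no penalty.

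**2. Change of unit.** Multiply concentration by k. The slope variance rescales by 1/k² and the covariance by 1/k, so V, the residuals, the fitted values and the p-values do not change. X becomes XD with D diagonal, and log det(X′V⁻¹X) rises by 2 ln det D:

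- linear: det D = k, shift 2 ln k
- quadratic: det D = k × k² = k³, shift 6 ln k
- log(Concentration/LLOQ): the ratio has no unit, shift 0

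| k | Linear | Quadratic | Log | Quadratic − linear | Linear − log |
|---|---|---|---|---|---|
| 100 | +9.21 | +27.63 | 0 | +18.42 | +9.21 |
| 1000 | +13.82 | +41.45 | 0 | +27.63 | +13.82 |

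Reporting testosterone in ng/mL and not ng/dL is k = 1/100, with the same shifts in the opposite direction.

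**3. Refit of the SAP model.** From the documents: 144 subjects (SAP 4.4) and five post-dose ECGs (protocol 7.3.5: Day 0 at 4 h, Day 28, Day 84 pre-dose and at 4 h, Day 168), with time point, centred baseline, and random intercept and slope.

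Assumed: median concentrations 20, 0.8, 0.3, 20 and 0.3 in a base unit called ng/mL; LLOQ 0.05; log-scale SDs 0.4 between and 0.5 within subjects; intercept SD 6, slope SD 0.15 and residual SD 9. The assumed true effects were 0.15c (linear), 0.5c − 0.006c² (quadratic) and 1.5 ln(c/LLOQ) (log).

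REML AIC in one data set per true form:

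| Truth | Unit | Linear | Quadratic (p) | Log | Rule selects |
|---|---|---|---|---|---|
| Linear | µg/mL | 5406.18 | 5389.43 (0.90) | 5432.35 | linear |
| Linear | ng/mL | 5419.99 | 5430.87 (0.90) | 5432.35 | linear |
| Linear | pg/mL | 5433.81 | 5472.32 (0.90) | 5432.35 | log |
| Quadratic | µg/mL | 5361.36 | 5322.59 (<0.0001) | 5389.25 | quadratic |
| Quadratic | ng/mL | 5375.17 | 5364.04 (<0.0001) | 5389.25 | quadratic |
| Quadratic | pg/mL | 5388.99 | 5405.49 (<0.0001) | 5389.25 | linear |

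The shifts between rows match step 2. In the first row AIC alone favours a quadratic term with p = 0.90 by 5406.18 − 5389.43 = 16.75; only the p-value condition stops it. In the last row a quadratic term with p<0.0001 ranks behind both other forms.

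ML AIC on the same data, identical in all three units (linear / quadratic / log):

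- linear truth: 5432.71 / 5434.70 / 5450.40, selects linear
- quadratic truth: 5387.33 / 5366.14 / 5406.90, selects quadratic

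**4. Full rule, 25 data sets per true form.** The p<0.05 condition is applied and the log form is always assessed.

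| Truth | Chosen in ng/mL | Chosen in pg/mL | Choice changed | Chosen by ML, any unit |
|---|---|---|---|---|
| Linear | linear 23, log 2 | log 17, linear 8 | 15/25 | linear 23, quadratic 2 |
| Quadratic | quadratic 16, linear 6, log 3 | log 16, linear 8, quadratic 1 | 21/25 | quadratic 23, linear 2 |
| Log | log 15, linear 10 | log 24, linear 1 | 9/25 | linear 13, log 10, quadratic 2 |

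**The case against.** The sponsor could make five points.

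- **The SAP does not say in words that the AIC comes from REML.** The code shown is the base linear model, and REML is right for its estimate. That is fair, but no other method appears anywhere, and a programmer following the plan would read AIC from the REML output.
- **AIC is not the only criterion.** The quadratic term needs p<0.05, which does not depend on units, and then only may be added; the log form is optional; and the final rule reads "The best model fit will be determined by the lowest AIC, unless the model results are not clinically or physiologically sensible". These limits are real: no unit can bring in a non-significant quadratic term. But the unit can still exclude a significant one, linear versus log has no p-value condition, and the override catches implausible results, not a plausible model picked for the wrong reason.
- **The unit will be fixed in practice.** Testosterone is in ng/dL throughout, and an assay reports in one unit. That makes the choice reproducible but not valid, since the comparison still contains an offset set by that unit.
- **No change in the QTcF estimate has been shown.** Correct: only the model choice was examined. How far the estimate at mean Cmax would move depends on the trial data.
- **No pass/fail bound rests on this model.** Also correct. The success rule in SAP 9.1 concerns testosterone, and the by-time-point QTcF summaries, outlier categories and morphology tables in SAP 11.5 do not use this model. This limits the consequence, not the error.

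**Conclusion.** The concern holds. As written, the rule compares REML AICs across models with different fixed effects, and the result depends on the unit of concentration. A factor of 1000 moves quadratic against linear by 27.6 AIC units and linear against log by 13.8; a factor of 100 moves them by 18.4 and 9.2. These shifts are exact and need no assumption about the data. How often the selected model changes (9 to 21 of 25 data sets between ng/mL and pg/mL) rests on the assumed concentrations, variances and effects and is an illustration only.

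The error affects the predicted changes in QTcF, HR, PR and QRS at mean Cmax in the separate ECG report. It does not affect the primary endpoint. It should be corrected because it bears on a stated secondary objective and the correction is almost free.

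**What to change.** Add a sentence to SAP 11.5 beside the code, for example: *Candidate forms with different fixed effects (linear, quadratic, log) will be fitted with METHOD=ML to the same records and compared by the resulting AIC; the selected form will then be refitted with METHOD=REML for the estimate and confidence interval.* The p<0.05 condition and the plausibility override can stay.

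Stating the concentration unit for each analyte would help reproducibility, but it does not replace the ML comparison.

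Cost: one sentence and one option in the SAS code. No new data, visits or assays are needed.
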